## 6.2.2. Analysis of Secondary Variables

The analysis of the following secondary endpoint will be described in this section.

The secondary endpoints are defined as follows:

- To calculate the specimen volume after BCL guided partial mastectomy, the water displacement method (WDM) will be used (results will be obtained within the same day of surgery).
- To compare the ideal specimen volume to the actual specimen volume and tumor volume, the tumor maximum diameter (mm) and tumor volume (mm^3) on supine MRI, and the ideal specimen volume (mm^3) will be recorded at V1;
- To record important clinical data on the removed specimens the presence of invasive cancer in core biopsy (Y/N), presence of DCIS in core biopsy (Y/N), presence of invasive cancer in lumpectomy specimen (Y/N), presence of DCIS in lumpectomy specimen (Y/N), subtype of invasive cancer (ductal vs lobular vs other), maximal tumor diameter (mm) on pathology report of lumpectomy specimen, shave biopsy done during surgery (Y/N and if done how many) will be recorded and checked.
- To evaluate the surgeon's perception of ease of use of the BCL system, a 5 Likert scale will be used at V2;
- To evaluate the patient's satisfaction, the BREAST-Q will be used at EOS/V4;
- To evaluate the safety and tolerability of BCL through physical examination and AEs assessment including the relationship of the AE to the BCL system at V1, V2, V3, V4.

### Collected Variables:

#### *Specimen and tumor volumes*

- Specimen volume determined by water displacement (ml) (number) [CRF –V2]
- Maximal tumor diameter on pathology report of lumpectomy specimen (cm) (number) [CRF –V2]

#### *Shave biopsies*

- Were any shave biopsies done? (Yes/No) [CRF –V2]
- If Yes, how many (number) [CRF –V2]
- What is the volume of shave biopsy determined by water displacement? (ml) (number) [CRF –V2]

#### *Cancer Characteristics in Biopsy and Lumpectomy*

- IBC or DCIS in lumpectomy specimen? (DCIS/IBC/Both) [CRF –V2]
- If invasive, subtype (Ductal/Lobular/Other) [CRF –V2]
- If other, please specify (free text) [CRF –V2]

#### *Likert Questionnaire for Ease of Use of BCL*

|  |                           |                  |                |
|--|---------------------------|------------------|----------------|
|  | Form               | Form Nr.  | 1M-DMST-011-A3 |
|  | Statistical Analysis Plan | Page      | 34 of 116      |
|  |                           | Version # | 0.1            |

- Did the investigator complete the Likert questionnaire? (Yes/No) [CRF – V2]
- If No, please specify the reason (free text) [CRF – V2]
- If Yes:
- 1. Overall, how satisfied or dissatisfied are you with the BCL device? (Very satisfied/Somehow satisfied/Neither satisfied nor dissatisfied/Somehow dissatisfied/Very dissatisfied) [CRF – V2]
- 2. How would you rate the ease of use of the BCL device? (Very easy/Easy/Neither easy nor complicated/Complicated/Very complicated) [CRF – V2]
- 3. How much, in your opinion, has the BCL device simplified surgery? (Very much/Somewhat/Neutral/Not really/Not at all) [CRF – V2]
- 4. How much, in your opinion, did the BCL device speed up surgery? (Very much/Somewhat/Neutral/Not really/Not at all) [CRF – V2]
- 5. How would you rate the safety of the BCL device? (Very high/High/Neither high nor low/Low/Very low) [CRF – V2]
- 6. How would you rate the reliability of the BCL device? (Very high/High/Neither high nor low/Low/Very low) [CRF – V2]
- 7. How likely would you be to reuse the BCL device? (Very likely/Likely/Neither likely nor unlikely/Unlikely/Very unlikely) [CRF – V2]
- 8. How likely would you be to recommend the use of the BCL device to your colleagues? (Very likely/Likely/Neither likely nor unlikely/Unlikely/Very unlikely) [CRF – V2]

#### *Likert Questionnaire for the Visualizer*

- Did the investigator complete the Likert questionnaire? (Yes/No) [CRF – V2]
- If No, please specify the reason (free text) [CRF – V2]
- If Yes:
- 1. Overall, how satisfied or dissatisfied are you with the Visualizer? (Very satisfied/Somehow satisfied/Neither satisfied nor dissatisfied/Somehow dissatisfied/Very dissatisfied) [CRF – V2]
- 2. How would you rate the clarity of the 3D tumor image created by the Visualizer? (Very high/High/Neither high nor low/Low/Very low) [CRF – V2]
- 3. How would you rate the reliability of the 3D tumor image created by the Visualizer? (Very high/High/Neither high nor low/Low/Very low) [CRF – V2]
- 4. How would you rate the ease of use of the Visualizer? (Very easy/Easy/Neither easy nor complicated/Complicated/Very complicated) [CRF – V2]
- 5. How much, in your opinion, did the Visualizer help surgery? (Very much/Somewhat/Neutral/Not really/Not at all) [CRF – V2]
- 6. How much, in your opinion, did the Visualizer speed up surgery? (Very much/Somewhat/Neutral/Not really/Not at all) [CRF – V2]
- 7. How likely would you be to reuse the Visualizer? (Very likely/Likely/Neither likely nor unlikely/Unlikely/Very unlikely) [CRF – V2]
- 8. How likely would you be to recommend the use of the Visualizer to your colleagues? (Very likely/Likely/Neither likely nor unlikely/Unlikely/Very unlikely) [CRF – V2]

|  |                           |                  |                |
|--|---------------------------|------------------|----------------|
|  | Form               | Form Nr.  | 1M-DMST-011-A3 |
|  | Statistical Analysis Plan | Page      | 35 of 116      |
|  |                           | Version # | 0.1            |

### *BREAST-Q*

- Did the subject complete the BREST-Q questionnaire? (Yes/No) [CRF – V4]
- If No, please specify the reason (free text) [CRF – V4]

If Yes:

#### *BREAST CANCER CORE SCALE (PREOPERATIVE): SATISFACTION WITH BREASTS:*

- A. How you look in the mirror clothed? (Very dissatisfied/Somewhat dissatisfied/Somewhat satisfied/Very satisfied) [CRF – V4]
- B. How comfortably do your bras fit? (Very dissatisfied/Somewhat dissatisfied/Somewhat satisfied/Very satisfied) [CRF – V4]
- C. Being able to wear clothing that is more fitted? (Very dissatisfied/Somewhat dissatisfied/Somewhat satisfied/Very satisfied) [CRF – V4]
- D. How you look in the mirror unclothed? (Very dissatisfied/Somewhat dissatisfied/Somewhat satisfied/Very satisfied) [CRF – V4]

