### 2.3.2 Secondary Endpoints

- To calculate the specimen volume after BCL guided partial mastectomy, the water displacement method (WDM) will be used (results will be obtained within the same day of surgery).
- To evaluate the surgeon's perception of ease of use of the BCL System, a 5 Likert scale will be used at V2;
- To evaluate the safety and tolerability of BCL through physical examination and AEs assessment including the relationship of the AE to the BCL System at V1, V2, V3, V4;
- To evaluate the patient's satisfaction, the BREAST-Q will be used at EOS/V4.

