### *Patient Satisfaction (BREAST-Q Assessment)*

|   |                           |                  |                |
|---|---------------------------|------------------|----------------|
|  | Form               | Form Nr.  | 1M-DMST-011-A3 |
|   | Statistical Analysis Plan | Page      | 38 of 116      |
|   |                           | Version # | 0.1            |

Patient-reported satisfaction will be evaluated using the BREAST-Q questionnaire. The scores of each answer range from 1 (worst answer) to 4 (best answer): the raw total scores for each module (preoperative and postoperative) will be calculated, then converted to Rasch scores (0–100) as per the BREAST-Q user's manual. Higher scores reflect greater satisfaction. Missing data will be imputed with the means of completed items if less than 50% of the scale items are missing, as per the manual guidelines. Results will be summarized in tables and figures, including a box plot of Rasch scores for visual comparison.

The evaluation of the secondary endpoint related to the assessment of the safety and tolerability of BCL, including physical examination and the assessment of adverse events (AEs) — as well as the relationship between the AEs and the BCL system — will be outlined in section 6.4, Safety Variables.

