| Listing 10. Specimen volumes                                | Listing of specimen and tumor measurements, including volumes collected pre-surgery (via supine MRI) and post-surgery (at visit V2).                        |
| Listing 11. Shave biopsies                                  | Listing of information on shave biopsies, number of shave biopsies performed, along with volume of the biopsy specimens determined by water displacement.   |
| Listing 12. Cancer characteristics in biopsy and lumpectomy | Listing of classification of cases identified as IBD, DCIS or both, and details of subtype classifications for invasive cases.                              |
| Listing 13. Likert questionnaire for ease of use of BCL     | Listing of Individual responses to all items from the Likert-scale questionnaire on the ease of use of the BCL system, as completed by investigators.       |
| Listing 14. Likert questionnaire for the Visualizer         | Listing of Individual responses to all items from the Likert-scale questionnaire on satisfaction with the Visualizer system, as completed by investigators. |
| Listing 15A. Breast-Q – pre-operative module                | Listing of Individual responses to all items from the pre-operative BREAST-Q and score, as completed by the patients.                                       |
| Listing 15B. Breast-Q – post-operative module               | Listing of Individual responses to all items from the post-operative BREAST-Q and score, as completed by the patients.                                      |

Patients' data will be represented as follows:

- |   |  |
|---|--|
| Figure 4. Tumor and specimen volumes | Box plot displaying the distribution of tumor and specimen volumes measures gathered across different stages of the study. |
| Figure 5. Tumor classification       | Bar chart displaying the cases identified as IBD, DCIS or both, and details of subtype classifications for invasive cases. |

|  |                           |                  |                |
|--|---------------------------|------------------|----------------|
|  | Form               | Form Nr.  | 1M-DMST-011-A3 |
|  | Statistical Analysis Plan | Page      | 40 of 116      |
|  |                           | Version # | 0.1            |

**Figure 6.** BREAST-Q scores

Box plot displaying the distribution of BREAST-Q Rasch scores from pre and post operative modules.

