### Listing 18B. Breast-Q – post-operative module

#### Full Analysis Set

| Screening number | A. How you look in the mirror clothed? | B. The shape of your lumpectomy breast when you are wearing a bra? | C. How normal you feel in your clothes? | D. Being able to wear clothing that is more fitted? | E. How your lumpectomy breast sits/hangs? | F. How smoothly shaped your lumpectomy breast looks? | G. The contour (outline) of your lumpectomy breast? | H. How equal in size your breasts are to each other? | I. How normal your lumpectomy breast looks? | J. How much your breasts look the same? | K. How you look in the mirror unclothed? | Pre-operative raw score | Pre-operative Rasch score |
|------------------|--|--|---|---|---|--|---|--|---|---|--|-------------------------|---------------------------|
| 01-001           | X                                      | X  | X                                       | X   | X   | X  | X   | X  | X   | X                                       | X  | XX                      | XX                        |
| XX-XXX           | X                                      | X  | X                                       | X   | X   | X  | X   | X  | X   | X                                       | X  | XX                      | XX                        |

|   |                           |                  |                |
|---|---------------------------|------------------|----------------|
|  | Form               | Form Nr.  | 1M-DMST-011-A3 |
|   | Statistical Analysis Plan | Page      | 105 of 116     |
|   |                           | Version # | 0.1            |

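### The SAP's preoperative BREAST-Q scale is scheduled only at V4, after surgery, so the descriptive pre/post display has no baseline as written

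*SAP*

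**What the plan says.** **Timing.** Protocol section 2.3.2 sets the endpoint: "To evaluate the patient's satisfaction, the BREAST-Q will be used at EOS/V4". Protocol sections 2.10.1, 2.10.2, 2.10.3 (flowchart) and 2.10.8, and SAP sections 1.2, 1.2.5 (flowchart) and 6.2.2, agree on V4. The protocol's visit lists for V0, V1 and V2 (sections 2.10.4 to 2.10.6) do not contain BREAST-Q. SAP section 5.4 puts V4 at 6 weeks ± 7 days after V2, the surgery visit.

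**Collection.** SAP section 6.2.2 lists one completion question for the whole instrument: "Did the subject complete the BREST-Q questionnaire? (Yes/No) [CRF – V4". It then lists a four-item preoperative core scale, headed "BREAST CANCER CORE SCALE (PREOPERATIVE): SATISFACTION WITH BREASTS", and an 11-item post-operative BCT module. All 15 items carry the V4 source tag. One preoperative item, for example, reads "B. How comfortably do your bras fit? (Very dissatisfied/Somewhat dissatisfied/Somewhat satisfied/Very satisfied) [CRF – V4".

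**Analysis.** The SAP derives a raw sum and a 0–100 Rasch score for each module, each with its own conversion table. It summarises the two modules in adjacent columns in the total-scores shell (headed Table 21B, indexed as 19B). The Patient Satisfaction text promises summaries "including a box plot of Rasch scores for visual comparison", and Figure 6 is described as "Box plot displaying the distribution of BREAST-Q Rasch scores from pre and post operative modules". No change score, paired analysis or test is planned.

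**The concern.** A scale labelled preoperative and shown beside a post-operative score will be read as a baseline. Under the written schedule both are completed at the same visit, weeks after the operation. The plan does not tell the patient which period the first four items refer to. Her answers could describe her state at V4, or a memory of her earlier state that may be affected by how the operation turned out. Neither is a baseline measurement.

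Patient satisfaction is a stated secondary objective, and protocol section 2.11.1 lists improved cosmesis and satisfaction among the anticipated benefits. A before-and-after picture without a true before could be taken as evidence on that benefit. Because protocol section 2.5.2 makes all secondary endpoints descriptive, the table and figure are themselves the reported result.

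**Working it through.** The documents give no numerical target for BREAST-Q, so there is no plan figure to reproduce. The check compares the schedules and then uses the SAP's own scoring table.

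1. **When V4 falls.** 6 weeks = 42 days. Window: 42 − 7 = 35 to 42 + 7 = 49 days after surgery.

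2. **Visit tags.** Preoperative items tagged to a visit before surgery: 0 of 4. Tagged to V4: 4 of 4. Post-operative items tagged to V4: 11 of 11. Completion questions: one, at V4. No schedule in either document shows an earlier administration.

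3. **Overlap of content.** Three of the four preoperative items have the same wording as post-operative items: A matches A (appearance in the mirror, dressed), C matches D (wearing closer-fitting clothes) and D matches K (appearance in the mirror, undressed). Under the written plan a patient answers these three twice at V4, once under each label.

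4. **What the conversion tables do if both modules describe the same state.** Suppose a patient gives the same answer, scored r = 1 to 4, to every item. The sums are 4r and 11r, and the SAP tables in section 6.2.2 convert them as follows:

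| r | Preoperative sum | Rasch | Post-operative sum | Rasch | Difference |
|---|---|---|---|---|---|
| 1 | 4 | 0 | 11 | 0 | 0 |
| 2 | 8 | 39 | 22 | 40 | 1 |
| 3 | 12 | 58 | 33 | 59 | 1 |
| 4 | 16 | 100 | 44 | 100 | 0 |

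Such a patient shows a difference of 0 or 1 point whatever surgery changed. This is an illustration for uniform answers about her state at V4. Mixed answers can give other differences, but those would reflect different items and scales, not change over time.

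5. **If she recalls instead.** Recall could raise or lower the preoperative score, so the display could overstate or understate a change. The documents contain nothing that fixes the direction or the size.

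**The case against.** The strongest reply is that little depends on this comparison. The endpoint is satisfaction at V4, not change from baseline, and the display is two summary columns and a box plot. That stands. A reader might infer that the satisfaction endpoint is lost. It is not, because the 11-item post-operative module answers it.

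A second reply is that the V4 tag may be a slip. The SAP is draft 0.1 and has other evident errors: systolic pressure lacks the V2 tag that diastolic pressure has (section 6.4.3), and the invasive-subtype rows in shell Table 17 repeat the IBC/DCIS categories. The CRF and the version 2.0 protocols on which the SAP is based were not available for this review. So the documents do not establish that every preoperative score was actually collected after surgery. They establish that the plan schedules it so, and the SAP's own flowchart and endpoint text agree with the tag. If the tag is wrong, it still needs correcting.

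Three further inferences are tempting:

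- **That a real loss of satisfaction would be hidden.** This follows only if patients answer about their current state. Under recall, a loss could equally be exaggerated.
- **That the bias can be sized in points or standard errors.** The documents give no standard deviation and no recall shift, and the standard error of a single mean is not the right yardstick for two same-day scores from the same patients.
- **That a within-patient change score is the remedy.** The two modules are a 4-item and an 11-item scale with separate conversion tables, and protocol Appendix 2 describes BREAST-Q scales as functioning independently. Nothing supplied shows that they share a metric.

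The post-operative listing shell (headed 18B, indexed as 15B) labels its total "Pre-operative raw score". That is a copying error and is not evidence about timing.

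**Conclusion.** The point holds as an inconsistency between label and schedule in a descriptive secondary display. As written, all four preoperative items fall 35 to 49 days after surgery, so the pre/post columns and Figure 6 have no baseline and could mislead in either direction. No hypothesis test, confidence interval or sample-size figure is affected, and satisfaction at V4 remains reportable.

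The conclusion rests on the SAP's visit tags and on the schedules in both documents. It assumes that the CRF was completed as those texts say, which only the CRF dates can confirm.

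**What to change.** 1. Check the actual completion dates of the four items against the CRF before the SAP is finalised. The SAP is still at version 0.1, and protocol section 2.5.2 requires version 1.0 before database lock.
2. **If they were completed before surgery:** correct the visit tag, the flowcharts and the endpoint text so that they show the pre-surgery visit.
3. **If they were completed at V4:** remove the preoperative column from shell Table 21B and the preoperative box from Figure 6. Remove the preoperative label from shell Table 20A and shell Listing 17A. Bring the section 6.2.2 text into line, report the post-operative score alone, and state that there is no baseline.
4. **For any patient not yet operated on:** give the four items at V0 or V1, with the flowchart and CRF changed to match. The SAP describes surgery in the past tense, so this may no longer apply.
5. In either case, change the total-score headings in shell Listing 18B to post-operative. Do not add a change score between the two scales.

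Steps 3 and 5 cost only SAP wording and shell edits. Dropping the comparison loses nothing valid, because without a baseline it could not show change. Step 4, if still possible, costs a four-item form at an existing visit and a minor amendment.

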#### *BCT MODULE (POSTOPERATIVE): SATISFACTION WITH BREASTS:*

- A. How you look in the mirror clothed? (Very dissatisfied/Somewhat dissatisfied/Somewhat satisfied/Very satisfied) [CRF – V4]
- B. The shape of your lumpectomy breast when you are wearing a bra? (Very dissatisfied/Somewhat dissatisfied/Somewhat satisfied/Very satisfied) [CRF – V4]
- C. How normal you feel in your clothes? (Very dissatisfied/Somewhat dissatisfied/Somewhat satisfied/Very satisfied) [CRF – V4]
- D. Being able to wear clothing that is more fitted? (Very dissatisfied/Somewhat dissatisfied/Somewhat satisfied/Very satisfied) [CRF – V4]
- E. How your lumpectomy breast sits/hangs? (Very dissatisfied/Somewhat dissatisfied/Somewhat satisfied/Very satisfied) [CRF – V4]
- F. How smoothly shaped your lumpectomy breast looks? (Very dissatisfied/Somewhat dissatisfied/Somewhat satisfied/Very satisfied) [CRF – V4]
- G. The contour (outline) of your lumpectomy breast? (Very dissatisfied/Somewhat dissatisfied/Somewhat satisfied/Very satisfied) [CRF – V4]
- H. How equal in size your breasts are to each other? (Very dissatisfied/Somewhat dissatisfied/Somewhat satisfied/Very satisfied) [CRF – V4]
- I. How normal your lumpectomy breast looks? (Very dissatisfied/Somewhat dissatisfied/Somewhat satisfied/Very satisfied) [CRF – V4]
- J. How much your breasts look the same? (Very dissatisfied/Somewhat dissatisfied/Somewhat satisfied/Very satisfied) [CRF – V4]
- K. How you look in the mirror unclothed? (Very dissatisfied/Somewhat dissatisfied/Somewhat satisfied/Very satisfied) [CRF – V4]

|  |                           |                  |                |
|--|---------------------------|------------------|----------------|
|  | Form               | Form Nr.  | 1M-DMST-011-A3 |
|  | Statistical Analysis Plan | Page      | 36 of 116      |
|  |                           | Version # | 0.1            |

### Derived Variables:

- Breast-Q score as foreseen by the scale's user's manual.

Sum of all items scores will be calculated for both preoperative and postoperative BREAST-Q module and converted into an equivalent RASCH transformed score (0-100). Higher scores reflect a better outcome.

| MODULE        | SUM SCORE | EQUIVALENT RASCH TRANSFORMED SCORE (0-100) |
|---------------|-----------|--|
| Preoperative  | 4         | 0  |
|               | 5         | 23   |
|               | 6         | 29   |
|               | 7         | 34   |
|               | 8         | 39   |
|               | 9         | 44   |
|               | 10        | 48   |
|               | 11        | 53   |
|               | 12        | 58   |
|               | 13        | 64   |
|               | 14        | 71   |
|               | 15        | 82   |
|               | 16        | 100  |
| Postoperative | 11        | 0  |
|               | 12        | 15   |
|               | 13        | 20   |
|               | 14        | 24   |
|               | 15        | 26   |
|               | 16        | 29   |
|               | 17        | 31   |
|               | 18        | 33   |
|               | 19        | 35   |
|               | 20        | 36   |
|               | 21        | 38   |
|               | 22        | 40   |
|               | 23        | 42   |
|               | 24        | 43   |
|               | 25        | 45   |
|               | 26        | 46   |
|               | 27        | 48   |
|               | 28        | 50   |
|               | 29        | 51   |
|               | 30        | 53   |
|               | 31        | 55   |
|               | 32        | 57   |
|               | 33        | 59   |
|               | 34        | 61   |
|               | 35        | 63   |
|               | 36        | 65   |
|               | 37        | 67   |
|               | 38        | 69   |
|               | 39        | 72   |
|               | 40        | 75   |

|  |                           |                  |                |
|--|---------------------------|------------------|----------------|
|  | Form               | Form Nr.  | 1M-DMST-011-A3 |
|  | Statistical Analysis Plan | Page      | 37 of 116      |
|  |                           | Version # | 0.1            |

|  |    |     |
|--|----|-----|
|  | 41 | 78  |
|  | 42 | 82  |
|  | 43 | 88  |
|  | 44 | 100 |

